6.3.11 Exposure to the Investigational Medicinal Product

Exposure to study drug will be listed [Listing 16.2.5.1.1 (Part A) and Listing 16.2.5.1.2 (Part B)] by subject within each study part and will include: Subject Number, Time Point, Treatment Received, Date/Time of Administration, Dose (unit), Partial Dose Taken and Comments.

6.3.12 Pharmacokinetic Concentrations and Variables

The analysis of the PK data will be based on the Pharmacokinetic Population (see section 6.2.3).

Concentrations below the (LLOQ) will be indicated by BLQ in the listings.

Pharmacokinetic concentration data will be listed [Listing 16.2.6.1.1 (Part A) and Listing 16.2.6.1.2 (Part B)] by subject including actual sampling times relative to dosing. Plasma concentrations will be summarized [Table 14.2.1.1 (Part A) and Table 14.2.1.2 (Part B)] within each part, by cohorts and nominal time point. The following descriptive statistics will be presented for plasma concentrations obtained at each nominal time point: n, arithmetic mean, SD, 95% CI of Arithmetic mean, coefficient of variation (CV%), geometric mean, 95% CI of Geometric mean, geometric SD, SD on log scale (SD(log)), geometric CV% (calculated as: $gCV\% = \text{SQRT}(e^{s^2}-1)*100$; where s is the standard deviation of the log-transformed values), median, minimum and maximum values.

Pharmacokinetic parameters will be listed [Listing 16.2.6.2.1 (Part A) and Listing 16.2.6.2.2 (Part B)] by subject and summarized [Table 14.2.2.1 (Part A) and Table 14.2.2.2 (Part B)] within each study part, and by cohorts, nominal timepoint. Descriptive statistics for calculated PK parameters will include: n, arithmetic mean, SD, 95% CI of Arithmetic mean, coefficient of variation (CV%), geometric mean, 95% CI of Geometric mean geometric SD, SD on log scale (SD (log)), geometric CV%. No descriptive statistics will be determined when fewer than three individual PK parameters are available.

Individual plasma concentration versus actual times will be plotted by cohorts of SAD [Figure 14.2.1.1.1 (Part A) and Figure 14.2.1.2.1 (Part A)] and MAD [Figure 14.2.1.1.2 (Part B) and Figure 14.2.1.2.2 (Part B)] parts including elderly male or post-menopausal females cohort for KM-819 in linear and semi-logarithmic scale.

Arithmetic (+/SD) mean and geometric mean plasma concentrations versus nominal times will also be presented in linear-linear scale of SAD [Figure 14.2.2.1.1 (Part A) and Figure 14.2.3.1.1 (Part A)], MAD [Figure 14.2.2.1.2 (Part B) and Figure 14.2.3.1.2 (Part B)] and young vs. elderly male or post-

PAREXEL International
Statistical Analysis Plan

menopausal females cohorts [Figure 14.2.2.2.1(Part A), Figure 14.2.2.2.2 (Part B) and Figure 14.2.3.2.1 (Part A), Figure 14.2.3.2.2 (Part B)].

Median plasma concentrations versus nominal times will also be presented in linear-linear scale (single ascending dose [Figure 14.2.4.1.1 (Part A)], multiple ascending dose [Figure 14.2.4.1.2 (Part B)] and young vs. elderly male or post-menopausal females cohorts [Figure 14.2.4.2.1 (Part A) , Figure 14.2.4.2.2 (Part B)].

All Single dose cohorts will be overlaid on the same plot. Similar plots will be generated for multiple dosing and young vs. elderly male or and post-menopausal females cohorts.

Individual urine concentration for SAD will be presented by cohort and subject [Listing 16.2.6.4 (Part A)].

6.3.12.1 Presentation of PK Data, Descriptive Statistics and PK Assessment

The following rules will be followed with regards to the number of decimal places and presentation of data in the tables and listings of concentration data:

- The individual concentrations will be reported to the same precision as the source data (for example, if the source data is presented to five significant digits, the individual values will be presented to five significant digits).
- The arithmetic mean, median, standard deviation (SD), geometric mean, geometric SD will be tabulated to one more significant digit compared to the source data, but with a maximum of four significant digits.
- Minimum and maximum values will be tabulated to the same precision as the source data, but with a maximum of four significant digits.
- 95% CI of Arithmetic mean and 95% CI of Geometric mean will be presented to two decimal places.
- Coefficient of variation (CV%) and geometric CV% will be presented to one decimal place.

The following rules will be followed with regards to the number of decimal places and presentation of data in the tables and listings of PK parameters:

PAREXEL International
Statistical Analysis Plan

- Individual PK parameters will be presented to four significant digits, with the exception of *tmax*, which will be presented to two decimal places. In addition, parameters directly derived from source data (e.g. *Cmax*,) shall be reported with the same precision as the source data (if this is not four significant digits).
- The arithmetic mean, median, standard deviation (SD), geometric mean, geometric SD will be reported to four significant digits, all other descriptive statistics will be reported to three significant digits except, coefficient of variation (CV%) and geometric CV% which will be presented to one decimal place.
- For *tmax* the minimum and maximum will be presented to two decimal places and the rest of the descriptive statistics to three decimal places.
- P-values will be presented to four decimal places.
- Estimates and confidence intervals (95% CI of Arithmetic mean and 95% CI of Geometric mean) in the form of percentages will be presented to two decimal places.
- Source data shall be used in all derived PK parameter calculations without prior rounding.

6.3.12.2 Handling of Values Below the Limit of Quantification (BLQ) in Concentration Summaries and Listings

Graphical presentation:

For graphs of arithmetic means all BLQ mean concentrations will be substituted by zeros. Graphs of geometric means include only time points with minimum concentration greater than zero. Any arithmetic mean that is BLQ will be excluded from log/linear presentation of arithmetic means. Any BLQ values prior to the last quantifiable concentration will be plotted at zero for individual linear/linear graphs and excluded from log/linear graphs. All BLQ values after the last quantifiable concentration will be excluded from individual linear/linear and log/linear graphs.

Handling of values below the limit of quantification (BLQ) in listings and for the calculation of descriptive statistics at each time point:

All concentrations below the limit of quantification (BLQ) or missing data will be labeled as such in the concentration data listings. Missing samples will be reported as no sample ("NS") and excluded from analysis. Values that are BLQ will be substituted with zero for the calculation of descriptive

PAREXEL International

Statistical Analysis Plan

statistics of concentration by time point and will be displayed as “not calculable” or NC for the calculation of statistical summaries.

6.3.12.3 Assessment of Dose Proportionality

For Part A, dose proportionality [Table 14.2.3.1 (Part A)] will be assessed for parameters C_{max} , $AUC_{(0-t)}$ and $AUC_{(0-inf)}$ and for Part B [Table 14.2.3.2 (Part B)] for parameters AUC_{tau} and C_{max} on Day 1 and Day 7 using the pharmacokinetic population via the power model.

Individual concentration values will be used to perform a least-squares linear regression analysis, using the formula $\log_{pkvar} = \beta_0 \times \log_{dose} + \beta_1$, where ‘ \log_{pkvar} ’ represents the natural log transformed C_{max} , AUC_{last} or $AUC_{(0-inf)}$ and ‘ \log_{dose} ’ represents the natural log transformed dose. An estimate of the slope of the regression line and corresponding 95% confidence interval (CI) will be obtained.

The following SAS code will be used:

```
PROC REG DATA=pkparam alpha=0.05;  
  MODEL log_pkvar = log_dose / CLB;  
  RUN;
```

For each of the parameters C_{max} , AUC_{last} , $AUC_{(0-inf)}$ of part A and C_{max} , AUC_{tau} of part B a plot of the log-transformed concentration against the log-transformed dose will be constructed including the fitted line from the linear regression and the line of unity.

Dose proportionality plots of individual primary PK parameters will be displayed versus dose (log-log scale) along with the regression line and the 95% CI [Figure 14.3.1.1 (Part A) and Figure 14.3.1.2 (Part B)]. Plots of dose-normalized parameters versus dose [Figure 14.3.2.1 (Part A) and Figure 14.3.2.2 (Part B)] will also be provided.

Additionally, an analysis of variance (ANOVA) [Table 14.2.4] of the natural log-transformed dose-normalized PK parameters $AUC_{inf}/dose$ and $C_{max}/dose$ with log-transformed KM-819 dose as a covariate and subject as random effect, will be performed to estimate the slope of the effect of dose level on the PK parameter and its 95% CI.

Proc Mixed Data = data;

By parameter;

PAREXEL International
Statistical Analysis Plan

Class Subject;

Model log (pk Parameter) = log (dose)/ ddfm = kr outp=pred;

Random subject;

Estimate 'Mean Log Slope' lgdose 1 /cl alpha=0.05;

Run;

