#### Part A, Single Ascending Dose (SAD)

Up to 40 healthy young adult male subjects and 8 healthy elderly male or post-menopausal female subjects will be enrolled and randomized to receive either KM-819 or placebo.

Each of the 5 dose escalation cohorts consists of 8 healthy young adult male subjects; 6 subjects will receive single dose of 10, 30, 100, 200, or 400 mg KM-819 and 2 subjects will receive placebo.

Cohorts will be dosed sequentially with escalating doses, escalation to the next dose level will take place only after the safety, tolerability data, and available PK data from the previously treated dose cohort has been reviewed; see Section 3.4 for dose escalation criteria. In each of the 5 single dose cohorts, dosing of subjects will be sentinel, i.e., 2 subjects will be dosed on the first day (1 subject will receive active treatment and 1 subject will receive placebo) and the remaining 6 subjects will be dosed at least 24 hours after the first 2 subjects.

After completion of the 5 dose escalation cohorts, 8 elderly male or post-menopausal female subjects will be enrolled into an additional cohort; 6 subjects will receive 200 mg KM-819 and 2 subjects will receive placebo.

[figure not shown]
See Table 3-1 for Part A dose groups.

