### **8.7.1 Dose Proportionality (Part A)**

Dose proportionality analysis will be performed as an exploratory analysis.

Dose proportionality for  $C_{max}$  and  $AUC_{inf}$  will be examined via the power model and will be summarized and reported graphically. The PK parameters and the dose will be logarithmically ( $\ln$ ) transformed prior to analysis. An alpha level of 5% will be used.

The power model assumes that the PK parameters are log-normally distributed with equal variances (constant coefficient of variation for untransformed data). A linear model with  $\ln$  (dose) as continuous independent variable will be estimated. Estimates of  $\beta_0$  and  $\beta_1$ , their standard

errors, 95% Confidence Interval (CI) and the CV for  $\beta_0$  for each PK parameter will be reported. Dose proportionality plots of individual primary PK parameters will be displayed versus dose (log-log scale) along with the regression line and the 95% CI. Plots of dose-normalized parameters versus dose will also be provided.

Additionally, an analysis of variance (ANOVA) of the natural log-transformed dose-normalized PK parameters  $AUC_{\text{inf}}/\text{dose}$  and  $C_{\text{max}}/\text{dose}$  with log-transformed KM-819 dose as a covariate and subject as random effect, will be performed to estimate the slope of the effect of dose level on the PK parameter and its 95% CI.

Further details will be provided in the SAP.

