6.2.2 Pharmacokinetic Population

The pharmacokinetic analysis set (PKAS) will be the primary analysis set for all PK displays and analyses, consists of all subjects from the SAF for whom sufficient plasma concentration data are available to facilitate the calculation of at least one PK parameter, had no important protocol deviations affecting the PK variables, as confirmed during a pre-analysis review of the data prior to database lock.

Data may/will be excluded (depending on the protocol and compound under study) from PK analysis (concentrations listed only) if any of the following criteria are fulfilled:

- Concomitant medication, which could render the plasma concentration-time profile unreliable

PAREXEL International

Statistical Analysis Plan

- The pre-dose concentration is greater than 5% of the corresponding C_{max} in any given treatment period (single dose cohort only).
- Subject vomits within 2 x the reported median T_{max} for the analyte (oral studies only).
- Subject has moderate or severe diarrhea within 2 x the reported median t_{max} for the analyte (oral studies only).

Any data excluded will be discussed in the CSR. Subjects who receive placebo will not be part of the PK analysis set.

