6.3.12.4 Time Invariance (Part B Only)

If data permits, the time invariance ratio will be calculated as the ratio of AUC(0- τ) on Day 7 to AUC(0- ∞) on Day 1 (If have reliable AUC(0- ∞) on Day 1) for each subject in each cohort. An ANOVA with terms for subject as a random effect and day as a fixed effect will be performed by dose on the loge-transformed AUC. Day will be treated as a class variable in the model. The time invariance of KM-819 will be assessed by calculating the ratio of the geometric least square means of AUC(0- τ) to AUC(0- ∞) and the corresponding 90% CI for each dose. AUC(0- ∞) on Day 1 will be considered as the reference phase in the analysis [Table 14.2.5].

An example of SAS code is included here.

ODS output solutionf=stat;

Proc Mixed;

by dose;

class subject day;

model logAUC = day / ddfm=kr;

random subject;

lsmeans day;

estimate 'test vs ref' day -1 1/cl alpha=0.1;

run;

The time invariance ratio will also be listed and summarized along with other PK parameters.

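### The dose-proportionality models pool the elderly 200 mg cohort with the young cohorts without an age term, and the Part B models run `by dose` merge the two 200 mg cohorts

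*SAP*

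**What the plan says.** **Population.** SAP 6.3.12.3 runs the dose-proportionality analysis "using the pharmacokinetic population via the power model". SAP 6.2.2 says this set "consists of all subjects from the SAF for whom sufficient plasma concentration data are available", subject to no important deviation affecting PK. The one treatment group removed by rule is placebo: "Subjects who receive placebo will not be part of the PK analysis set". Age is not a criterion. The SAP's figure list confirms the reading, because its young-versus-elderly plots are labelled with the pharmacokinetic population.

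**Models.** The power-model code is "MODEL log_pkvar = log_dose / CLB". It is applied to Cmax and AUC in both parts. The dose-normalised ANOVA (Part A only) is fitted "with log-transformed KM-819 dose as a covariate and subject as random effect". Neither has an age, sex or cohort term. Protocol 8.7.1 calls the analysis exploratory, adds "An alpha level of 5% will be used", and does not limit it to young subjects.

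**Elderly cohorts.** In Part A, "8 elderly male or post-menopausal female subjects will be enrolled into an additional cohort; 6 subjects will receive 200 mg KM-819", a dose also given to a young cohort. In Part B, Protocol 3.1 and the SAP's Table 2 give 200 mg, but the SAP's design text leaves the dose to the investigator and sponsor.

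**Part B repeated-dose models.** SAP 6.3.12.4 says the time-invariance ANOVA "will be performed by dose on the loge-transformed AUC", with subject random and day fixed. SAP 6.3.12.5 fits a day slope with a random subject intercept. Both example programs use `by dose`.

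**The concern.** The objectives separate ascending doses in young men from single and multiple doses in elderly men and post-menopausal women. These models do not. The elderly subjects all sit at one dose above the mean log dose, so if their exposure differs from that of young men at the same dose, a regression on dose alone attributes part of the difference to dose. The slope and its interval are the main output of the analysis, and the distortion appears only when the elderly differ, which is what their cohort can reveal.

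In the repeated-dose models the risk is different. A single 200 mg result from 12 active subjects may describe neither population, and the elderly cohort gets no model-based estimate of its own, although its PK is a separate secondary objective.

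**Working it through.** The documents give no expected slope, exposure ratio or variability, so there is no stated figure to reproduce. The elderly/young exposure ratio R and the between-subject CV below are assumptions.

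**Inputs (Protocol Tables 3-1 and 3-2).** Six active subjects per cohort. Part A: young at 10, 30, 100, 200 and 400 mg plus elderly at 200 mg, 36 in all. Part B: young at 30, 100, 200 and 400 mg plus elderly at 200 mg, 30 in all, taking each day's values as a separate fit.

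**Slope bias.** With x = ln(dose), least squares gives

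bias = ln(R) x 6 x (ln 200 - mean x) / Sxx.

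- Part A: mean x = 4.483, ln 200 = 5.298, Sxx = 57.27. Factor = 6 x 0.8155 / 57.27 = 0.0854.
- Part B: mean x = 4.919, Sxx = 23.04. Factor = 6 x 0.3794 / 23.04 = 0.0988.

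| R | Part A bias | Part B bias |
|---|---|---|
| 0.8 | -0.019 | -0.022 |
| 1.25 | +0.019 | +0.022 |
| 1.5 | +0.035 | +0.040 |
| 2 | +0.059 | +0.068 |

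At R = 1.5 the fitted 10-to-400 mg exposure ratio in Part A is too high by a factor of 40^0.0346 = 1.136. The dose-normalised ANOVA has the same bias: dividing by dose only subtracts 1 from the slope, and with one value per subject the random subject term cannot separate age from dose.

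**Coverage of the 95% CI.** At CV 30% the log-scale SD is sqrt(ln 1.09) = 0.294, so the Part A slope SE is 0.294 / sqrt(57.27) = 0.0388. The bias at R = 1.5 is 0.0346 / 0.0388 = 0.9 SE. Simulated Part A coverage (60,000 data sets per setting):

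| CV | R = 1 | R = 1.25 | R = 1.5 | R = 2 |
|---|---|---|---|---|
| 20% | 95% | 92% | 88% | 84% |
| 30% | 95% | 93% | 91% | 86% |
| 50% | 95% | 94% | 93% | 90% |

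In Part B with the elderly at 200 mg, coverage stays between 94% and 96% throughout. The SE is larger (0.0612 at CV 30%, so the bias at R = 1.5 is 0.040 / 0.0612 = 0.65 SE), and the unmodelled difference inflates the residual variance. At CV 30% the interval is about 1.11 times the young-only width at R = 1.5 and 1.34 times at R = 2.

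**Dependence on the Part B elderly dose.** The factor would be -0.216 at 30 mg, -0.047 at 100 mg and +0.197 at 400 mg.

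**Models run `by dose`.** These have no dose coefficient; they estimate a day effect within subjects. In a simulated stratum of 6 young and 6 elderly, shifting every elderly value by ln 1.5, ln 2 or ln 3 left the day slope at -0.0072 (90% CI -0.0217 to 0.0074) each time. A different time course does get through: an elderly slope of 0.06 per day against zero in the young raised the pooled slope to 0.0228, an increase of 0.030, half the difference. For time invariance, equal numbers give the geometric mean of the two ratios: young 1.00 and elderly 1.25 give sqrt(1.25) = 1.118; young 1.00 and elderly 1.5 give sqrt(1.5) = 1.225.

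**Cost of separating the groups.** Elderly subjects at one dose carry no slope information once age group is in the model, so the young-only fit and the age-term fit share the same Sxx: 52.48 (Part A) and 21.96 (Part B). The SE ratios to the planned fit are sqrt(57.27 / 52.48) = 1.045 and sqrt(23.04 / 21.96) = 1.024.

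**The case against.** The strongest reply has four parts.

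- **Low stakes.** Dose proportionality is exploratory, with no acceptance limit for the slope and no decision attached. The elderly cohorts follow the young escalation cohorts, so these fits cannot affect that escalation. This stands, and it limits the weight of the point.
- **Small, assumed effect.** Only 9 to 10% of the log exposure difference reaches the slope, and the documents supply neither R nor CV. This also stands. No sentence says that the slope is meant for young men only; that is an inference from the objectives.
- **Ambiguous stratum.** SAP 6.3.1 uses cohort and dose almost as one label, SAP 6.3.12.4 computes individual ratios per cohort, and the code is offered as an example. Separate strata may have been intended. But the code as written merges the two 200 mg cohorts, and the text does not correct it.
- **Reported elsewhere.** Individual time-invariance ratios are to be summarised with the other PK parameters, which SAP 6.3.12 does by cohort, and young-versus-elderly concentration figures are planned. A marked difference would probably be seen there. That softens the loss but does not correct the slope or supply a steady-state estimate for the elderly.

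A reader might infer that the Part B models run `by dose` also turn age or sex differences into a dose effect. They do not: no dose effect is estimated, and the random subject term absorbs a level difference. Nor does the loss of coverage extend to Part B at 200 mg.

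**Conclusion.** As written, the power model (Parts A and B) and the Part A dose-normalised ANOVA include the elderly cohort with nothing to absorb an age or sex difference. The slope takes up 0.085 x ln(R) in Part A and, if the elderly dose is 200 mg, 0.099 x ln(R) in Part B. Under an assumed R of 1.5 and CV of 30%, that is +0.035 with coverage of about 91% in Part A, and +0.040 with coverage near 95% in Part B. With R = 1 there is no bias. For the repeated-dose models the point is narrower: one 200 mg estimate would average two populations if their accumulation or time course differs. The problem is modest and confined to exploratory and descriptive PK results, but it changes what the reported numbers mean and is cheap to remove before database lock.

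**What to change.** - **SAP 6.3.12.3:** restrict the power model and the dose-normalised ANOVA to the young adult cohorts, or add an age-group term. The slope has the same Sxx either way. The term keeps more residual degrees of freedom (33 against 28 in Part A, 27 against 22 in Part B) and estimates the age-group contrast, but assumes a common residual variance. Since the elderly cohort may include women, that contrast is age and sex combined.
- **SAP 6.3.12.4 and 6.3.12.5:** replace `by dose` with `by cohort` in text and code, so that the elderly cohort has its own estimate.
- **Part B elderly dose:** reconcile the SAP's design text, which leaves it open, with the SAP's Table 2 and Protocol 3.1, which give 200 mg.

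The programming cost is one filter or one model term, and one BY variable. The statistical cost, if exposure does not differ, is a slope SE larger by 4.5% in Part A (0.0388 to 0.0405 at CV 30%) and 2.4% in Part B (0.0612 to 0.0626). The 200 mg repeated-dose estimates would rest on 6 subjects each, as at the other doses.

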#### *1.2.1.3 Pharmacokinetics*

A pharmacokinetic (PK) study in male rats, by administering single intravenous (IV) injection of 5 mg/kg KM-819 showed:  $C_{max}$ : 62.73 ug/ml,  $t_{max}$ : 0.083 hr, and  $t_{1/2}$ : 7.08 hr. Single dose oral administration of 5 mg/kg KM-819 resulted in:  $C_{max}$ : 3.89 ug/ml,  $t_{max}$ : 3 hr, and  $t_{1/2}$ : 6.06 hr. Oral bioavailability assessed by comparing  $AUC_{0-\infty}$  for oral and IV administration was 35.97%.

A PK study in male dogs, by administering single IV injection of 1 mg/kg KM-819 showed:  $t_{max}$ : 0.08 hr,  $C_{max}$ : 11.91 ug/ml, and  $t_{1/2}$ : 8.61 hr. Single dose oral administration of 5 mg/kg and 10 mg/kg KM-819 resulted in:  $t_{max}$ : 0.83 hr and 0.58 hr,  $C_{max}$ : 6.01 ug/ml and 9.48 ug/ml, and  $t_{1/2}$ : 4.96 hr and 5.03 hr, bioavailability: 32.3% and 28.9%, respectively.

In vitro plasma protein binding is 99.96 %, 99.79%, and 99.96% in rat, dog and human, respectively. KM-819 at 10 uM did not inhibit CYP450s (including 1A2, 2C9, 2C19, 2D6, 3A4) and P-gp.

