### ***3.5.1 PK stopping criteria***

Due to the liver damage (higher ALT, ALP, GGT, and enlargement in common bile duct in liver) reported in one male dog following multiple dosing at 2000 mg/kg for 7 days, and NOAEL in male and female beagle dog at 1000 mg/kg/day for 14 days, the decision to escalate to the next planned dose will be based on review of PK exposure data from previous dose cohort(s). This will involve use of best available modeling practices of the observed AUC (i.e.,  $AUC_{\text{tau}}$  or  $AUC_{0-\infty}$ ) and  $C_{\text{max}}$  from each dose, resulting in a predictive distribution of AUC and  $C_{\text{max}}$  at higher dose levels. If predicted mean AUC and  $C_{\text{max}}$  for the next dose level is higher than 41.3 ug.h/mL and 9.3 ug/mL, respectively, then the dose escalation will stop and the Sponsor and PI will need to review the totality of data, including safety and PK before make any dose escalation decision. This PK stopping criteria are based on dog 2-Week study NOAEL exposure at 1000 mg/kg/day (the most conservative species and gender).

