6.3.2 Statistical Significance Level

All statistical tests will be two-sided and will be performed at the 5% level of significance, unless otherwise stated.

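### In Part A the additional dose-normalised ANOVA repeats the power model (slope minus 1, same standard error) with a subject variance that cannot be separated from the residual, so there is no formal check that one slope fits

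*SAP*

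**What the plan says.** Protocol 8.7.1 and SAP 6.3.12.3 plan two model-based analyses of dose proportionality.

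- **Power model.** A least-squares regression of the log PK parameter on log dose, coded as "MODEL log_pkvar = log_dose / CLB".
- **Additional analysis.** Protocol 8.7.1 introduces it as "analysis of variance (ANOVA) of the natural log-transformed dose-normalized PK parameters"; it covers two of them, AUCinf and Cmax, each divided by dose. The SAP gives the model terms and the purpose this way: "with log-transformed KM-819 dose as a covariate and subject as random effect, will be performed to estimate the slope of the effect of dose level". The sample PROC MIXED code has subject in the CLASS statement, dose as a continuous term, a random subject effect and Kenward-Roger degrees of freedom. The SAP's table list (Table 14.2.4) assigns it to Part A.

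SAP 6.3.12.3 also plans a log-log plot "including the fitted line from the linear regression and the line of unity", log-log plots of individual parameters with the regression line and its 95% CI, and plots of dose-normalised parameters against dose. SAP 6.1.3 (Table 1) derives AUCinf, AUClast and Cmax divided by dose, and SAP 6.3.12 summarises PK parameters by cohort with geometric means and 95% CIs.

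On status, Protocol 8.7.1 states: "Dose proportionality analysis will be performed as an exploratory analysis". SAP 6.3.2 sets the level: "All statistical tests will be two-sided and will be performed at the 5% level of significance".

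**The concern.** Calling the second analysis an ANOVA and presenting it as additional suggests that it tests dose proportionality in another way, for example by comparing dose levels. As specified, it does not. Dose enters as a continuous log covariate, so the model is again a straight line on the log-log scale. A reader of the study report would see two tables that agree and could take the second as corroboration of the first.

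What is lost is a test of the assumption that both tables share. If exposure flattens or bends within 10 to 400 mg, one slope averages over the bend. It can then suggest a loss at doses where there is none, or stay close to 1 while exposure departs from proportionality. The random subject term is a separate specification error, because Part A gives it nothing to estimate from.

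**Working it through.** The documents state no slope, power or CV for dose proportionality, so there is no planned figure to reproduce.

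**Inputs.** Five young-adult doses (10, 30, 100, 200, 400 mg) with 6 active subjects each, so 30 records (Protocol 3.1). Six active elderly subjects at 200 mg make 36 if they are included. Placebo subjects are outside the PK set (SAP 6.2.2). Earlier participation in a KM-819 study is an exclusion (Protocol 4.2, No. 2), so each subject contributes one dose. Two-sided alpha is 0.05. CVs of 30%, 40% and 50% are assumed.

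**1. Slope identity.** Let x = ln(dose), y = ln(PK) and z = ln(PK/dose) = y − x.
- Power slope: b = Σ(x − x̄)y / Sxx.
- Dose-normalised slope: Σ(x − x̄)(y − x) / Sxx = b − 1.
- The residuals of the two fits are identical, so SE, CI width and p-value are identical too (testing b = 1 in the first, b − 1 = 0 in the second).
- Simulated example, n = 30: 0.9117 (95% CI 0.821 to 1.002) against −0.0883 (−0.179 to 0.002), with SE 0.0443 and p = 0.0559 for both. The difference was also 1 with 36 records.

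This follows the SAP text. The sample MODEL statement shows the log parameter without dose normalisation. Run literally, it would return the power slope itself. Its ESTIMATE line also names a variable (lgdose) that is not in the MODEL statement.

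**2. Subject effect.** With one record per subject, the covariance matrix is (σ²subject + σ²residual) × I, so only the sum enters the likelihood. In a simulated Part A data set the REML log-likelihood was −12.8421 whether 0%, 10%, 50%, 90% or 99.9% of the variance was assigned to subject. Slope and SE did not change and equalled least squares.

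**3. What one slope does under an assumed plateau.** Take AUC proportional to 200 mg, with 400 mg giving the same AUC as 200 mg.
- Sxx = 6 × Σ(x − x̄)² = 52.48.
- Slope fitted to the means: 0.8675. Since 10^(0.8675 − 1) = 0.737, the fit implies a 26% loss of dose-normalised AUC at 100 mg relative to 10 mg, where the assumed truth has none.
- The 95% CI of the slope still includes 1 in about 25%, 44% and 58% of trials at CV 30%, 40% and 50%.

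**4. Lack-of-fit test in the same scenario.** Five levels less two parameters give 3 df, with 30 − 5 = 25 error df (31 with the elderly).
- Residuals of the means from the fitted line: −0.129, 0.017, 0.176, 0.268, −0.333. Six times their sum of squares is 1.385.
- σ² = ln(1 + CV²) = 0.0862, 0.1484, 0.2231.
- Noncentrality 1.385/σ² = 16.1, 9.3, 6.2.
- Power from the noncentral F(3, 25): 88.9%, 65.3%, 46.6%.

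**5. Other assumed shapes** (2,000 simulations each, CV 30% and 50%).
- Log-log slope 1 to 100 mg, then 0.5: lack-of-fit power about 63% and 27%.
- Slope 1.3 to 100 mg, then 0.2: the fitted slope is 0.92 and its CI includes 1 in about 90% of trials at either CV. Lack-of-fit power is above 99% and about 90%.
- True single slope: the test rejects in 4% to 5%.

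**6. Line of unity.** Proportionality is slope 1 with any intercept. Predicted CL/F is 2.93/0.35 = 8.37 L/h (Protocol 5.3). In mg and mg·h/L, y = x lies 8.4-fold above exactly proportional data. In ng·h/mL it lies 1000/8.37 ≈ 119-fold below.

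**The case against.** The identity and the unidentifiable split are not in dispute. The case on the other side concerns consequence, and much of it stands.

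- **A reader might infer that nothing in the plan would reveal curvature.** The documents do not support that. Dose-normalised plots and by-cohort geometric means are planned, and a plateau as in step 3 would halve the dose-normalised value at 400 mg in both. What is missing is a formal or model-based check.
- **A reader might infer that the second analysis gives wrong results.** It does not. Total variance, slope and SE are estimable and equal least squares. The practical risks are a redundant table, a software warning and unreliable degrees of freedom.
- **A reader might infer a plateau from the dog data.** Single oral doses of 5 and 10 mg/kg gave Cmax of "6.01 ug/ml and 9.48 ug/ml" (Protocol 1.2.1.3), while the limits derived from 1000 mg/kg/day are "41.3 ug.h/mL and 9.3 ug/mL, respectively" (Protocol 3.5.1). These come from different studies and regimens. The bioavailabilities in 1.2.1.3 (32.3% and 28.9%) imply AUC rising 2 × 28.9/32.3 = 1.79-fold for a doubled dose. This is at most a weak hint of less-than-proportional absorption.
- **Power can be made to look better than it is.** A contrast of 400 mg against all lower doses detects the assumed plateau in about 99.9%, 96% and 87% of trials, but it is built to match that scenario. The planned slope CI already excludes 1 in about 75%, 56% and 42%. The lack-of-fit test's 89%, 65% and 47% are a smaller gain, though it answers a different question.
- **Use of the slope.** The documents do not say that later studies will predict from it. Protocol 1.3 says only that the study's data will guide later dosing, and escalation uses separate exposure modelling (Protocol 3.5.1).
- **The line of unity** may already mean a slope-1 reference line, since the SAP does not define it. It affects one plot and no estimate.

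**Conclusion.** The point holds in a limited form. For AUCinf and Cmax on the same Part A records, the additional ANOVA is exactly the power model with its slope shifted by 1. This is algebra and needs no assumption about the drug. The random subject variance is not identifiable, but the slope is unaffected. Both inferential analyses presuppose one constant slope, so neither can test it, and the check is left to inspection of plots and summaries.

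The size of what could be missed depends on assumed shapes and CVs. In the worked plateau, a single slope implies a false 26% loss between 10 and 100 mg. In the steeper-then-flatter shape, its CI covers 1 in about 90% of trials. The documents do not establish either shape. The analysis is exploratory in a study whose primary objective is safety and tolerability. The change is therefore worth making because it is cheap and adds information, not because a main conclusion is at risk.

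**What to change.** In SAP 6.3.12.3, with a matching note against Protocol 8.7.1:

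1. Replace the additional ANOVA by one on ln(AUCinf/dose) and ln(Cmax/dose) with dose level as a class effect and no random subject term. Make the code match: dose-normalised response, dose in the CLASS statement.
2. Report geometric mean ratios of each dose level to a prespecified reference level with 95% CIs, and a lack-of-fit test of the power model (3 df for five levels; number of levels minus 2 if doses are added or dropped).
3. Label both as exploratory and of limited power, so that a non-significant lack-of-fit test is not read as proof of a single slope.
4. State whether the elderly 200 mg cohort is included. Error df are 25 without it and 31 with it.
5. Define the line of unity as a slope-1 line with fitted intercept, through the mean of the logged data, and not y = x.

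The cost is SAP wording and a few lines of code. No new data, subjects or assessments are needed.
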